5.3.2 Laboratory Data

Laboratory tests will be reported separately for hematology, blood chemistry and serum quantitative immunoglobulins (Ig).

For the purposes of presentation in both tables and listings, the following laboratory test results will be converted to the International System of Units (SI) before presentation: sodium, potassium, chloride, bicarbonate (or CO₂), albumin, total protein, creatinine, uric acid, calcium, phosphorus, magnesium, glucose, total and direct bilirubin, alkaline phosphatase, red blood cell (RBC) count, hemoglobin, hematocrit, platelets, white blood cell count (WBC) with 5-part differential performed manually or by flow cytometry (lymphocytes, neutrophils, monocytes, basophils, and eosinophils), amylase, lipase, alanine aminotransferase (ALT), aspartate aminotransferase (AST), IgA, IgM and IgG. Laboratory tests will be graded according to CTCAE Version 5.0.

If a laboratory test value is reported using a non-numeric qualifier (e.g., less than [<] a certain value or greater than [>] a certain value), the given numeric value will be used in the summary statistics, ignoring the non-numeric qualifier.

For continuous laboratory results, descriptive statistics will be provided by visit for observed value and change from baseline. Plots of mean observed value over time will be produced for continuous laboratory test results.

For laboratory tests graded by CTCAE, the following summary tables will be created by treatment arm:

- Summary of worst post-baseline value on treatment, regardless of baseline value according to the following categories:
 - Any grade
 - Grade 1-2
 - Grade 3-4
 - Grade 3
 - o Grade 4
- Summary of worst post-baseline value on treatment that represents a worsening in grade from baseline (shift table) according to the following categories:
 - Any grade
 - Grade 1-2
 - Grade 3-4
 - o Grade 3
 - o Grade 4

In addition, laboratory tests with Grade 3 or 4 laboratory values will be presented in a separate patient listing.

Laboratory tests with bi-directional grades (e.g., hyperglycemia and hypoglycemia) will be presented separately for each direction within each by grade summary table.

For laboratory tests not graded by CTCAE, the following summary tables will be created by treatment arm:

- Summary of worst post-baseline value on treatment, regardless of baseline value according to the following categories:
 - Low (less than lower limit of normal)
 - Normal (greater than or equal to lower limit of normal and less than or equal to upper limit of normal)
 - High (greater than upper limit of normal)
- Summary of worst post-baseline value on treatment that represents a worsening from baseline (shift table) according to the following categories:
 - Low (less than lower limit of normal)
 - Normal (greater than or equal to lower limit of normal and less than or equal to upper limit of normal)
 - High (greater than upper limit of normal)

Patients with more than one post-baseline abnormality will be counted once for each type of abnormality (low, high). Only patients with no low or high abnormalities reported will be classified as normal.

5.3.3 Vital Signs

The actual values of vital sign parameters, including temperature, heart rate, weight and systolic and diastolic blood pressure, will be presented in a by-patient listing. Blood pressure will be summarized as follows by treatment arm:

- Descriptive statistics, for systolic and diastolic blood pressure separately
 - Baseline value
 - Maximum on-treatment value
 - Change from baseline to maximum on-treatment value
- Categorical summary of baseline value, maximum on-treatment value for systolic and diastolic blood pressure separately, with categories defined as follows:
 - Diastolic blood pressure
 - <80 mm Hg

 - 80 89 mm Hg
 - 90 or higher mm Hg
 - Systolic blood pressure
 - <120 mm Hg

 - 120 129 mm Hg
 - 130 139 mm Hg
 - 140 or higher mm Hg
- Categorical summary of baseline value, maximum on-treatment value for systolic and diastolic blood pressure combined using the categories define above (*i.e.*, diastolic <80 mm Hg and systolic <120 mm Hg, diastolic <80 mm Hg and systolic 120 – 129 mm Hg)

Heart rate will be summarized as follows by treatment arm:

- Descriptive statistics for baseline value, minimum on-treatment value, maximum on treatment value, change from baseline to maximum on-treatment value
- Categorical summary of baseline value, minimum on-treatment value, maximum on-treatment value, with categories defined as follows:
 - <60 bpm
 - \circ 60 100 bpm
 - <100 bpm

Plots of mean observed value over time will be produced for diastolic blood pressure, systolic blood pressure, heart rate and temperature.

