Abbreviations: AE = adverse event; BID = twice daily; CMV = cytomegalovirus; d = day; D = Study Day; ECOG = Eastern Cooperative Oncology Group; EOT = End-of-Treatment; HIV = human immunodeficiency virus; HTLV-1 = human T-lymphotropic virus type 1; M = month; PD = progressive disease; PO = orally; Q2M = every 2 months; SAE = serious adverse event;  $\beta$ -hCG =  $\beta$ -human chorionic gonadotropin.

- 1. See Section 6 for additional information on each assessment.
- 2. Screening evaluations other than clinical laboratory tests performed within 7 days of C1D1 do not need to be repeated at C1D1 (predose). C1D1 laboratory tests do not need to be repeated if performed within 72 hours prior to Screening.
- 3. All laboratory samples on C1D1 should be collected predose.
- 4. Additional visits may be scheduled / procedures may be performed at the Investigator's discretion, as clinically indicated.
- 5. The End-of-Treatment (EOT) visit is to be performed within 7 days after the last study drug dose. If safety assessments were performed within the previous 2 weeks, they need not be performed at the EOT visit. If disease response assessments were performed within the previous 4 weeks, they need not be performed at the EOT visit.
- 6. Patients who discontinue treatment from duvelisib for reasons other than PD are to have disease response assessments performed Q2M per Table 3 until the development of PD, as determined by the Investigator, death, or initiation of alternate anti-cancer therapy.
- 7. After development of PD, as determined by the Investigator, patients are to be followed Q3M for survival; this follow-up may be conducted via telephone.
- 8. Vital signs, including temperature, blood pressure, and heart rate, are to be measured only if clinically indicated.

- 9. Screening serology includes assessment of CMV serologies and a liver serology panel. HIV and HTLV-1 tests are to be performed during Screening for all patients without documentation of prior negative results (see Section 6.10.1 for details).
- 10. Urine or serum β-human chorionic gonadotropin pregnancy testing is to be performed for women of childbearing potential. Pregnancy testing is to be repeated as deemed necessary by the Investigator.
- 11. Tumor biopsy from Screening or archival tumor tissue will be collected to evaluate prognostic markers. In the event a bone marrow biopsy is collected at Screening please provide a sample.

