# Table 2:Expansion Phase Schedule of Events

						Cycle / Day	y						
	Screen-		Cycle 1	Cycle 1		Cycle 2		Cycle 4 and then every 2 cycles (WCBP only)13	Cycle 5 and then every 2 cycles 	End of Treat- ment (EOT) 	Safety Follow- up	PD Follow- Up 	Survival Follow- up 
Procedure 	ing D-30 to -1 	D1 	D8 ± 3	D15 ± 3	D1 ± 3	D15 ± 3	D1 ± 3		D1 ± 4	≤7 d from last dose	30 + 7 d from last dose	Q2M (± 1M)	Q3M (± 1M)
Provision of written informed consent	X												
Demographics	X												
Medical History, including cancer history	X												
Archival Slides, initial pathological diagnosis	X 												
12-lead electrocardiogram9	X												
Echocardiogram 	X												
Complete physical examination	X									X			
Targeted physical examination		Х			X		X		X		X	See Table 4	
Vital signs 	X	Х	X	X	X	X	X		X	X	X		
Screening serology 	X												
CD4 lymphocyte cell count (local laboratory)	X												
Blood chemistry	X	X	X	X	X	X	X		X	X	X		
Hematology	X	X	X	X	X	X	X		X	X	X		
β-hCG pregnancy test 	Х	Х			Х		Х	Х	Х	X	Х		

						Cycle / Day	7						
	Screen-		Cycle 1			Cycle 2		Cycle 4 and then every 2 cycles (WCBP only)13	Cycle 5 and then every 2 cycles 	End of Treat- ment (EOT) 	Safety Follow- up	PD Follow- Up 	Survival Follow- up 
Procedure 	ing D-30 to -1 	D1 	D8 ± 3	D15 ± 3	D1 ± 3	D15 ± 3	D1 ± 3		D1 ± 4	≤7 d from last dose	30 + 7 d from last dose	Q2M (± 1M)	Q3M (± 1M)
Serum Immunoglobulins	X	X					Х		X	X			
Tumor tissue	X 												
Blood for pharmacodynamic assessment		X 				X 							
Blood for pharmacokinetic assessment								See Table 5	5				
Blood for exploratory biomarkers 	X	Х			X		Х		X			X	
Response Assessments				•				G T 11			1		
ECOG Performance Status								See Table 4	ł				
Concomitant medications & Procedures			All con	All concomitant medications and procedures are to be documented from 30 days before the Screening visit through 30 days after the last study drug dose								X	
AE/SAE assessment			All AEs	All AEs are to be documented at the time written informed consent is provided through 30 days after the last study drug dose									
Study Drug Administration				Duvelisib is to be administered PO BID continuously in 28-day cycles									

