Survival status													Х

Abbreviations: AE = adverse event; BID = twice daily; CMV = cytomegalovirus; d = day; D = Study Day; ECOG = Eastern Cooperative Oncology Group; EOT = End-of-Treatment; HIV = human immunodeficiency virus; HTLV-1 = human T-lymphotropic virus type 1; M = month; PD = progressive disease; PO = orally; Q2M = every 2 months; SAE = serious adverse event;  $\beta$ -hCG =  $\beta$ -human chorionic gonadotropin.

1. See Section 6 for additional information on each assessment.

- 2. Screening evaluations other than clinical laboratory tests performed within 7 days of C1D1 do not need to be repeated at C1D1 (predose). C1D1 laboratory tests do not need to be repeated if performed within 72 hours prior to Screening.
- 3. All laboratory samples on C1D1 should be collected predose.
- 4. Additional visits may be scheduled / procedures may be performed at the Investigator's discretion, as clinically indicated.

- 5. The End-of-Treatment (EOT) visit is to be performed within 7 days after the last study drug dose. If safety assessments were performed within the previous 2 weeks, they need not be performed at the EOT visit. If disease response assessments were performed within the previous 4 weeks, they need not be performed at the EOT visit.
- 6. Patients who discontinue treatment from duvelisib for reasons other than PD are to have disease response assessments performed Q2M per Table 4 until the development of PD, as determined by the Investigator, death, or initiation of alternate anti-cancer therapy.
- 7. After development of PD, as determined by the Investigator, patients are to be followed Q3M for survival; this follow-up may be conducted via telephone.
- 8. Stained Formalin-fixed, paraffin-embedded (FFPE) slides used for PTCL diagnosis must be collected for all patients enrolled and submitted for central pathology review. See lab manual for details.
- 9. Additional on-treatment or follow-up electrocardiograms should be performed at the Investigator's discretion as clinically indicated.
- 10. Additional on-treatment or follow-up echocardiograms should be performed at the Investigator's discretion as clinically indicated.
- 11. Vital signs, including temperature, blood pressure, pulse, and respiration rate, and weight (kg) are to be measured. Height (cm) to be measured only at Screening.

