# 6.9. Vital Signs, Height and Weight

Vital signs, including temperature (°C), blood pressure, pulse, and respiration rate, as well as weight (kg) will be measured at the time points specified in the Schedule of Events (Table 1 and Table 2). Height (cm) will be measured during Screening only.

Systolic and diastolic blood pressure and pulse will be measured with the patient in a supine or sitting position; the same position will be used for a patient throughout the study. Blood pressure should be assessed on the same arm throughout the study.

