#### **11.10.** Safety Analyses

Safety analyses will be performed on the Safety population, and safety endpoints will be tabulated and presented.

AEs will be coded using the Medical Dictionary for Regulatory Activities (MedDRA) for purposes of summarization. All AEs occurring during the study will be included in by-patient data listings and tabulated by MedDRA system organ class and preferred term. Adverse events will be summarized overall, by relationship and by severity. Events leading to death, SAE, and events resulting in treatment discontinuation will be listed and, if warranted by the data, tabulated.

Exposure to study drug and study drug compliance will be tabulated.

A by-patient listing of ECOG performance status data will be prepared.

The actual value and change from Baseline to each on-study evaluation will be summarized for vital sign measurements, as warranted by the data. By-patient listings of vital sign measurements will be prepared.

Individual patient laboratory parameter values and summary statistics over time will be prepared using descriptive statistics. Severity of select clinical laboratory measures will be determined using NCI CTCAE criteria and Grade 3 or 4 laboratory values will be presented in a separate patient listing.

The use of concomitant medications, coded using World Health Organization Drug Dictionary, will be included in by-patient listing.

Additional safety analyses may be performed to most clearly enumerate rates of toxicities and to further define the safety profile of duvelisib.

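### SAP 5.3.3 tabulates on-treatment blood pressure and heart rate only as extremes against one baseline reading, a change that grows with the number of readings and should not be compared across phases; the top heart-rate category is also misprinted.

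*SAP*

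**What the plan says.** **Collection.** In Dose Optimization, Table 1 marks vital signs at Screening, C1D1, C2D1, C4D1 and every second cycle after that, End of Treatment (EOT) and Safety Follow-up. Its footnote 8 adds: "Vital signs, including temperature, blood pressure, and heart rate, are to be measured only if clinically indicated". In Expansion, Table 2 marks the same kinds of visit plus C1D8, C1D15 and C2D15, with later readings at C3D1, C5D1 and every second cycle. Its footnote 11 carries no such condition: "Vital signs, including temperature, blood pressure, pulse, and respiration rate, and weight (kg) are to be measured". Protocol 6.9 covers both phases and says vital signs "will be measured at the time points specified in the Schedule of Events (Table 1 and Table 2").

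**Analysis planned in the protocol.** Section 11.10: "The actual value and change from Baseline to each on-study evaluation will be summarized for vital sign measurements". The sentence goes on to make this conditional on the data warranting it.

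**Analysis planned in the SAP.** Section 5.3.3: "Blood pressure will be summarized as follows by treatment arm". The listed statistics are the baseline value, the maximum on treatment and the "Change from baseline to maximum on-treatment value", with categories of the baseline and maximum values. Heart rate is treated in the same way, with the minimum added. Mean observed values are plotted over time and individual values are listed, but change from baseline by visit is not tabulated. The three heart-rate categories are under 60, 60 to 100, and under 100 bpm.

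**The concern.** One noisy reading (the last before the first dose, SAP 4.7) is set against the largest of several. That change has a positive expected value even when the drug does nothing, and it increases with the number of readings and so with time on treatment. A reader of the table could take it for a drug effect.

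The number of readings also differs by phase by design. Where Dose Optimization readings depend on a clinical indication, they are a selected sample as well. Columns for the two phases placed side by side would then not measure the same thing. The by-visit summary in Protocol 11.10 does not depend on the count of readings, but SAP 5.3.3 leaves it out without saying so. Protocol 11.1 says that departures from the protocol's analyses will be indicated in the SAP.

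Separately, the heart-rate categories as written have no place for a rate above 100 bpm, and the third overlaps the first two.

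**Working it through.** The documents give no figure for vital signs to reproduce. The check has three steps.

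**1. Scheduled post-baseline readings.** Inputs are the X marks in Tables 1 and 2. C1D1 predose is taken as baseline, EOT is left out at first, and every Table 1 mark is assumed to be carried out.

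| Up to | Dose Optimization | Expansion |
|---|---|---|
| End of Cycle 2 | 1 (C2D1) | 4 (C1D8, C1D15, C2D1, C2D15) |
| C4D1 | 2 | 5 |
| C6D1 | 3 | 6 |
| C9D1 | 4 | 8 |

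**2. Expected change to maximum with no drug effect.** Assume independent normal readings around a constant patient mean, with within-patient SD s. The baseline error averages zero, so

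E[max of k readings − baseline] = s × e(k), where e(k) = ∫ x · k · φ(x) · Φ(x)^(k−1) dx.

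Numerical integration gives:

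| k | 1 | 2 | 3 | 4 | 5 | 6 | 8 |
|---|---|---|---|---|---|---|---|
| e(k), in SD units | 0 | 0.56 | 0.85 | 1.03 | 1.16 | 1.27 | 1.42 |

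The documents give no SD. For an assumed s of 6 to 12 mm Hg (unrounded e(k) used throughout), the mean change to maximum is 3.4 to 6.8 mm Hg with 2 readings and 7.6 to 15.2 with 6.

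**3. Difference between phases from the counts alone.** This is s × [e(k Expansion) − e(k Dose Optimization)].

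| Up to | k | Difference in SD | mm Hg at s = 6 to 12 |
|---|---|---|---|
| End of Cycle 2 | 1 vs 4 | 1.03 | 6.2 to 12.4 |
| C4D1 | 2 vs 5 | 0.60 | 3.6 to 7.2 |
| C6D1 | 3 vs 6 | 0.42 | 2.5 to 5.1 |
| C9D1 | 4 vs 8 | 0.39 | 2.4 to 4.7 |

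Adding one EOT reading to each side at the end of Cycle 2 makes it 2 vs 5, or 3.6 to 7.2 mm Hg.

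The categorical table behaves in the same way. In a simulation with an assumed mean systolic pressure of 125 and between-patient SD of 12, the share with a maximum of 140 or more, for 1 vs 4 readings, is 13.1% vs 24.2% at s = 6 and 18.8% vs 42.5% at s = 12.

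These figures treat every reading as taken on schedule. They do not model readings triggered by a clinical indication, which could raise the Dose Optimization maximum.

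**The case against.** The case for leaving 5.3.3 alone has real weight:

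- Worst on-treatment value is this SAP's own safety convention. SAP 5.3.2 uses it for laboratory data, and it finds individual extremes that visit means can hide.
- The tables are descriptive. Protocol 11.4 keeps the primary and secondary analyses of the two phases separate, and no test between phases is planned. Cohorts 1 and 2 share one schedule, so the schedule argument does not touch the only randomised contrast, although time on treatment may still differ.
- Time information is not lost, because 5.3.3 keeps mean plots and a listing. Protocol 11.10 was conditional.
- Vital signs are not a named endpoint, and blood pressure and heart rate are not among the risks in Protocol 1.4.

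All of this stands, and it limits the consequence. It does not answer the central point: the only tabulated change from baseline is one that is biased upward, and the plots show observed values, not change.

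Three stronger readings are tempting, and the documents do not support them.

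- **Dose Optimization had no required vital signs.** Footnote 8 read alone says so, but the X marks and Protocol 6.9 say otherwise. The documents contradict each other, and they show a plan, not what was collected.
- **Expansion maxima will be the higher ones.** Fewer readings lower the Dose Optimization maximum, but indication-triggered readings may raise it. The net direction is unknown.
- **Tachycardia will be hidden.** It would be missing from the categorical table only. The maximum-value statistics and the listing still show it. A conversion error in the category text cannot be fully excluded, although greater-than signs survive elsewhere in the SAP.

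**Conclusion.** The point holds as a minor one. SAP 5.3.3 gives a change from baseline that is positive on average without a drug effect once a patient has two or more on-treatment readings: about 0.56 within-patient SD with 2 and 1.27 with 6. Scheduled readings differ by phase, 1 against 4 by the end of Cycle 2 on the most favourable reading of Table 1, so the maxima should not be compared across phases.

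The counts come from the documents. The SD multiples rest on independent normal readings with a constant mean, and the mm Hg and percentage figures also rest on assumed SDs and an assumed mean. The sign of any difference between phases is not established. No primary result and no formal test is affected. The category misprint is a separate, small error.

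**What to change.** In SAP 5.3.3:

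1. Keep the maxima (and the heart-rate minimum) as an outlier display, and label them so.
2. Add the Protocol 11.10 summary: actual value and change from baseline at each scheduled visit, by phase and treatment, in the format SAP 5.3.2 already uses for laboratory data. This removes the bias from unequal counts. It does not remove any selection from readings taken only when indicated.
3. Show the number of on-treatment readings per patient beside the maxima, with a footnote that maxima are not comparable across phases.
4. Change the third heart-rate category to above 100 bpm.

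In addition, reconcile Table 1 footnote 8 with Protocol 6.9 and state in the SAP which instruction governed collection in Dose Optimization.

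Reducing Dose Optimization to a listing, or cutting the maxima off at an early visit, is not advised. Either would discard safety information, and Protocol 1.3 is concerned with toxicities of later onset.

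Cost: one extra table and SAP wording; no new data.

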5.3.4 ECOG Performance Status

A by-patient listing will be presented for ECOG performance status data.

5.3.5 Electrocardiogram (ECG)

A by-patient listing will be presented for ECGs. Per the protocol, ECGs are to be collected at baseline.

5.3.6 Echocardiogram

A by-patient listing will be presented for echocardiogram baseline and post-baseline assessments (if any)

5.3.7 Concomitant Medications and Procedures

Please refer to Section 5.1.6 for the definition and summary of concomitant medications. Concomitant procedures will not be summarized. A by-patient listing will be presented.

5.3.8 Deaths

On-treatment deaths are defined as deaths that occur within 30 days of the last dose of study medication. Deaths on treatment and causes for deaths occurring on treatment, deaths occurring prior to progression, and deaths during follow-up will be summarized.

A by-patient listing of deaths on study will be presented.

5.3.9 Pregnancy Test

A by-patient listing of pregnancy test results will be presented.

5.4 Pharmacokinetic Analyses

Pharmacokinetic analyses will be conducted on the Safety Analysis Set.

Blood samples will be taken for the analyses of duvelisib and possible metabolite(s) in plasma at the time points defined in the schedule of assessments. The relevant PK parameters will be determined using bioanalytical data.

Presentation of PK data will include:

- Descriptive statistics (n, mean, standard deviation, %CV, median, minimum, maximum) will be presented in tabular form by cohort, cycle and day.
- Linear-linear and log-linear plots of mean and median by nominal time will be presented by cohort, cycle and day.

PK analysis will be repeated for the subset of enrolled Japanese patients and non-Japanese patients. The Japanese patients will be presented separately for the Safety run-in patients (first 6 Japanese patients treated) and expansion phase patients (remaining expansion phase Japanese patients).

